## 10.6.4 Vital Signs

Each vital sign will be summarized by treatment and by visit, using descriptive statistics (n, mean, median, SD, minimum, maximum) for the safety population for diastolic blood pressure, systolic blood pressure for both standing and supine position, heart rate and respiratory rate.

The latest non-missing vital sign value collected prior to dosing will be used as the baseline values. The baseline values will usually be the vital signs recorded at the baseline visit. In the case of repeated vital signs, the last collected values within that visit will be used for the summary tables.

Vital signs will be provided in a data listing by treatment group, subject, visit and parameter.

## 10.6.5 Physical and Neurological Examination

The physical and neurological examination normal/abnormal results will be listed by treatment group, subject, visit and parameter.

[figure not shown]
### 10.6.6 Columbia-Suicide Severity Rating Scale

Count and percentage of C-SSRS responses will be generated over the visit. This summary will also be produced for each disease type and AChEI usage within disease type.

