#### 4.3 Exclusion Criteria

- 1. Subjects at modified Hoehn-Yahr stage 5.
- 2. History of significant neurologic disease, other than PDD or DLB that may affect cognition, or concurrent neurological disease diagnosed at the time of onset of dementia.
- 3. Subject has had neurosurgical procedure for treatment of PD (such as deep brain stimulation implant), or if such procedure is anticipated or planned during the study period.
- 4. History of brain magnetic resonance imaging (MRI) scan indicative of any other significant abnormality, which would explain a dementing process other than PDD or DLB. Note: a new MRI scan is required if not done at or since the initial diagnosis of PD; a repeat MRI scan is required if there have been intervening changes to the subject's clinical presentation in the past 12 months. CT scan is acceptable for subjects fitted with a non-MRI-safe cardiac pacemaker, or other relevant medical reason, with Medical Monitor approval.
- 5. History of unexplained loss of consciousness, or epileptic fits (unless febrile).
- 6. Inability to hear or differentiate the 2 different tones necessary for auditory ERP P300 assessment, using the centrally provided ERP equipment; subjects who wear a hearing aid must remove their hearing aid during the screening auditory test and during ERP P300 recordings.
- 7. Diagnosis with current symptoms of severe major depressive disorder (GDS score [15-item scale] > 7 at Screening). In discussion with the Medical Monitor, subjects with a GDS score between 8 and 10 inclusive can be considered for study participation if the increased score is driven by specific domains related to the pandemic and its restrictions, rather than by major depression.
- 8. Significant suicide risk as defined by suicidal ideation based on the C-SSRS within the last 12 months, at Screening and on Day 1 (i.e., a 'yes' response to Question 4 or 5, or any specific behaviors).
- 9. Significant psychosis (according to the Diagnostic and Statistical Manual of Mental Disorders, [5th edition; DSM-5; American Psychiatric Association, 2013]) interfering with

- the ability of the subject to complete study procedures in the judgment of the investigator, for reasons such as requirement to reduce previously stable dopaminergic therapy.
- 10. Moderate or severe substance abuse disorder (according to DSM-5; American Psychiatric Association, 2013).

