### 8.4.4 Columbia-Suicide Severity Rating Scale

Results from the C-SSRS questionnaire will be listed and summarized using descriptive statistics by treatment group and visit.

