#### 6 STUDY DESIGN CONSIDERATIONS

This study (ATH-1017-PD-0201) is designed to demonstrate as a safety and proof of concept study of ATH-1017 in PDD and DLB subjects. Eligible participants will receive once daily (OD) subcutaneous (SC) injections of ATH-1017 (40 mg or 70 mg) or placebo, over a 26-week double-blind period, followed by a 4-week safety follow-up.

NOTE: This study was stopped early; safety listings and summaries will be performed as previously envisioned; however efficacy and biomarker analyses will be exploratory in nature.

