#### 9 OVERALL STATISTICAL CONSIDERATIONS

#### 9.1 General Conventions

Efficacy and safety data will be summarized and presented by disease type (PDD or DLB), acetylcholinesterase inhibitor (AChEI) usage within disease type, treatment group, and time point in summary tables. Continuous variables will be presented by descriptive statistics: n, mean, standard deviation (SD), median, minimum, and maximum. Categorical variables will be tabulated by frequency count and percentage. Percentages are based on the number of subjects in each treatment group in the given population for AE summary tables, and additionally overall for medical history, prior and concomitant medications. For all other tables, percentages are based on the number of subjects with non-missing data in each treatment group and overall for the given population.

Means, medians and percentiles will be displayed to one more decimal place than the data, dispersion statistics (e.g., standard deviation) will have two more decimal places, and the minimum and maximum will be displayed to the same number of decimal places as reported in the raw data. Percentages will be displayed with one decimal place. P-values will be quoted to 4 decimal places consistent with SAS PVALUEw.d format set to PVALUE6.4. P-values < 0.0001 will be presented as p<0.0001.

Listings will include all subjects with defined analysis population for each listing. Listings will generally be sorted by disease type, treatment, subject ID, parameter and visit date/study day. Unscheduled visits will also be included in the listings.

Days will be converted to weeks by dividing by seven. Days will be converted to months by dividing by 30.44. Days will be converted to years by dividing by 365.25. All data collected during the study will be analyzed and reported except as stated otherwise.

All data will be analyzed using the SAS® Version 9.4 or later.

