#### 9.2 Baseline Definition

For safety summaries, the last pre-randomization measurement is defined as the baseline value. For clinical effect measures baseline is defined as the last pre-randomization measurement.

GST score, ADCS-CGI-C, and CaGI-C are change scores, so no further calculation is required. Appendix 1 describes calculation of the baseline GST score for baseline covariate purposes. For all other efficacy measures, baseline is the average of all measurements prior to first dosing, or if only one measurement exists that value will be used.

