- a If 28 days is not sufficient to complete the Screening period, the possibility of an extension can be discussed with the Medical Monitor.
- b Only weight collected at Baseline/Day 1 (Visit 2b), Week 12 (Visit 5), Week 26 (Visit 8), and Safety follow-up (Visit 9).
- Urine pregnancy test will be performed for females with child-bearing potential at screening.
- d Blood collection for FSH levels (to confirm post-menopausal state in females), serology, genotyping, fT3, fT4, and TSH.
- 'C-SSRS Baseline/Screening' version will be administered at Screening and 'C-SSRS Since Last Visit' version will be administered at all post-Screening visits.
- f Dispensing of kits containing study drug will occur every 2 weeks; drug returns will be recorded and compliance calculated. Larger provision of study drug is permitted to accommodate personal need, e.g., vacation; site should check in with subject/caregiver via phone approximately every 2 weeks in cases of larger dispensing. IMP administration by the caregiver will be assessed at Visits 2b through 8, inclusive.
- g First SC injection of IMP will be performed at site under supervision; subject should withhold IMP dose on the day of subsequent clinic visits (IMP administration will be done on site under supervision of site staff; training of proper injection techniques for subject/caregiver will be performed as needed); subjects will remain at site for 2 hours ± 15 minutes for safety observation follow up after first SC injection of IMP.
- h Physical and neurological exam to be done post-dose at all visits where subjects are dosed.
- i MRI (or CT) scan if not done since the initial diagnosis of PD.
- j 12-lead ECGs will be performed pre-dose and 30 (± 15) minutes post-dose on Day 1(Visit 2b) and 30 (± 15) minutes post-dose at all other visits. All ECG assessments will be performed in triplicate.
- Vital signs (systolic and diastolic BP, orthostatic BP, HR, respiratory rate, and body temperature) will be performed pre-dose on all visits. Supine BP and HR recordings will be made after the subject has been supine for at least 5 minutes. Orthostatic BP will be recorded as follows: the first blood pressure will be the average of 3 measurements recorded after the subject is supine for 5 minutes; the second blood pressure will be recorded after the subject stood for up to 3 minutes.
- 1 Safety labs include chemistry, hematology, urinalysis, and coagulation.
- m Prior and concurrent medications.

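### C-SSRS is summarised only by visit, so no planned table gives the number of subjects per arm with any suicidal ideation or behaviour on treatment

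*SAP*

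**What the plan says.** C-SSRS belongs to the primary safety endpoint (Protocol section 2; SAP Table 1). SAP 10.6.6 gives the analysis in two sentences: "Count and percentage of C-SSRS responses will be generated over the visit" and "This summary will also be produced for each disease type and AChEI usage within disease type". The general conventions in SAP 9.1 break safety data down further, by "treatment group, and time point in summary tables". Protocol 8.4.4 is in line with this and adds a listing: "Results from the C-SSRS questionnaire will be listed and summarized using descriptive statistics by treatment group and visit". SAP 10.6.6 does not repeat the listing, but SAP section 6 keeps it after the early stop, since "safety listings and summaries will be performed as previously envisioned".

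Two other places bear on the point.

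- **Form.** The schedule footnotes in SAP Appendix 2 state "C-SSRS Baseline/Screening' version will be administered at Screening and 'C-SSRS Since Last Visit' version will be administered at all post-Screening visits". Only the Screening record therefore comes from the Baseline/Screening form. Day 1 and all later visits use the Since Last Visit form.
- **Windows.** SAP 9.6 assigns unscheduled and early-termination assessments to the nearest scheduled visit. For non-efficacy data it keeps the last record in the window. The C-SSRS window for Week 12 is Days 64 to 98.

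Neither document defines a count of subjects with any post-dose ideation or behaviour, a worst post-dose category, or a shift from baseline for C-SSRS.

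**The concern.** The first safety question about C-SSRS is how many subjects in each arm had suicidal ideation or behaviour while on drug. SAP 10.6.1 answers the matching question for adverse events, counting subjects with one or more events. For C-SSRS there is no such summary, only separate rows by visit.

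The rows have two further weaknesses. They do not cover equal lengths of time, so a rise or fall across visits mixes risk with look-back. They can also lose a positive answer when a later form falls in the same window. That is a realistic route here, because the trial stopped early and Appendix 2 requires all safety outcomes at early termination however recent the last assessment was. The documents do not say how many such visits occurred.

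**Working it through.** The documents give no C-SSRS rate, so there is no planned figure to reproduce.

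**1. Look-back at each visit.** The scheduled days (Appendix 2) are 1, 14, 42, 84, 112, 140, 182 and 210. Look-back is the difference between successive days. The range uses the ±7-day visit windows, with Day 1 fixed.

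| Visit | Nominal look-back (days) | Range with windows (days) |
|---|---|---|
| Week 2 | 14 − 1 = 13 | 6 to 20 |
| Week 6 | 42 − 14 = 28 | 14 to 42 |
| Week 12 | 84 − 42 = 42 | 28 to 56 |
| Week 16 | 112 − 84 = 28 | 14 to 42 |
| Week 20 | 140 − 112 = 28 | 14 to 42 |
| Week 26 | 182 − 140 = 42 | 28 to 56 |
| Week 30 (off drug) | 210 − 182 = 28 | 14 to 42 |

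**2. What the rows say about subjects.** If visit v has n(v) positives, the number of distinct subjects lies between the largest n(v) and the sum of the n(v), capped at the arm size. Take the planned 25 per arm and one positive at each of the six on-treatment visits. The lower bound is 1/25 = 4% and the upper bound 6/25 = 24%. All six rows read 4% in either case. This needs no assumption about how ideation behaves over time.

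**3. Loss of a positive.** Suppose a form is positive on Day 84 and an early-termination form is negative on Day 95. Both days lie in Days 64 to 98. The Day 95 form is kept, although it looks back only 95 − 84 = 11 days, and the Week 12 row shows no positive for that subject.

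**4. Size of the look-back effect (illustration; all rates are assumptions).** Suppose new ideation arises at a constant rate of 2% per 4 weeks. The daily rate is r = −ln(0.98)/28, and the chance of a positive form is 1 − exp(−r × look-back).

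- Week 2: 0.9%. Weeks 6, 16 and 20: 2.0%. Weeks 12 and 26: 3.0%.
- Ratio of Week 12 to Week 2, from unrounded values: 2.98/0.93 = 3.2.
- Any time from Day 1 to Day 182: 1 − exp(−181r) = 12.2%, about 3 of 25.

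For assumed rates of 1% to 10% per 4 weeks, the any-time figure runs from 6.3% to 49.4%. The highest single-visit figure runs from 1.5% to 14.6%, and the ratio stays at 3.1 to 3.2.

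The ratio depends on ideation being new at each report. If a fraction f of subjects has persistent ideation, the chance becomes f + (1 − f) × the value above. With 2% new per 4 weeks and f of 2%, 4% or 8%, the ratio falls to 1.7, 1.4 or 1.2.

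**The case against.** A fair defence has five parts.

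- **The data are not lost.** Counts are planned as well as percentages, and Protocol 8.4.4 requires a listing, which SAP section 6 keeps. SAP 9.1 also puts unscheduled visits in the listings, so a replaced positive can still be seen there. This stands. A hand count from a listing is still not a planned summary.
- **Clinically important cases have another route.** Protocol 6.4.1.1 treats clinically significant abnormal safety assessments as adverse events, and SAP 10.6.1 counts those per subject. This stands in part, because not every positive answer becomes an adverse event.
- **Arms share one form and one schedule.** A reader might infer from the unequal look-backs that the drug-placebo comparison is biased. The documents do not support that. At a given visit the nominal look-back is the same in every arm, and a rise due to look-back would show on placebo too.
- **Baseline plays no part in the planned output.** SAP 9.2 says "For safety summaries, the last pre-randomization measurement is defined as the baseline value", which would normally pick the short Day 1 form, while eligibility refers to "Significant suicide risk as defined by suicidal ideation based on the C-SSRS within the last 12 months, at Screening and on Day 1". A reader might infer that subjects with ideation at Screening will be reported as free of it at baseline. SAP 10.6.6 plans no shift or change from baseline, so no planned C-SSRS output does this. It becomes relevant only if a shift is added.
- **The trial is small and stopped early.** SAP section 8 plans minimal analyses and no statistical conclusions. In the 2% scenario, 25 subjects give an expected 0.23 positives at Week 2 and 0.75 at Week 12, both below one person. The look-back effect on trends could hardly be seen. That weakens the trend argument but not the missing subject count.

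**Conclusion.** The point holds as a gap in the planned summaries. SAP 10.6.6 gives no number of subjects per arm with any on-treatment ideation or behaviour, and that number cannot be derived from the by-visit rows. With one positive of 25 at each of six visits, the true figure could be anywhere from 4% to 24%. The last-record rule in SAP 9.6 can also remove a positive from a row. Both conclusions follow from the documents without any assumed rate.

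The look-back point is secondary. Trends across visits, and any contrast with the Screening form, are hard to interpret for new or episodic ideation. Three stronger statements might be inferred and should not be made:

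- That percentages must rise about threefold at Weeks 12 and 26. The 3.2 ratio needs constant-rate, non-persistent ideation at nominal visit spacing.
- That Screening must exceed every later visit. Subjects were already filtered there under exclusion criterion 8.
- That a subject positive at several visits is counted several times in one figure. Each row counts a subject once, and nothing planned sums the rows.

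**What to change.** In SAP 10.6.6, add one subject-level table by arm giving:

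- subjects with any suicidal ideation, by worst category, and subjects with any suicidal behaviour;
- all post-dose records through Week 26, including unscheduled and early-termination forms, with this table stated to be exempt from the last-record rule in SAP 9.6;
- Week 30 shown separately, as it is off drug.

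Keep the by-visit counts as supporting output, and do not place the Screening form in the same trend as the later visits. If a shift is shown, define baseline for it as the worst of Screening and pre-dose Day 1. Appendix 2 allows C-SSRS at any time during a visit, so the shift definition should also say how a Day 1 form completed after dosing is classed.

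The cost is some SAP wording and one table shell. No new data are needed, and the only drawback is an extra table in a small, stopped trial.

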#### 10.6.7 Geriatric Depression Scale

Descriptive statistics for the results of GDS will be presented over the visit. This summary will also be produced for each disease type and AChEI usage within disease type.

Confidential Page 40 of 57

Confidential Page 41 of 57

# 12 APPENDICES

Confidential Page 44 of 57

# Appendix 1. Derivation of GST scores.

A composite approach will be utilized to derive the GST score for each patient at each visit in order to support an overall assessment of disease based on the combination of the clinical and functional scores (change from baseline ADAS-Cog13 and change from baseline ERP P300 latency).

The following notation will be used to compute the GST score. Let  $x_{ijk}$  and  $y_{ijk}$  will denote the changes from baseline to the kth visit for the jth patient in the ith trial arm (i=1 corresponds to placebo and i=2 corresponds to ATH-1017) for ADAS-Cog13 and ERP P300 latency, respectively. To simplify notation, it will be assumed that the number of patients in a trial arm does not depend on the visit, i.e.,  $n_1$  patients in the placebo arm and  $n_2$  patients in the ATH-1017 arm.

The GST score will be computed by applying the following algorithm to the ADAS-Cog13 and ERP P300 latency change scores. Beginning with ADAS-Cog13, the overall mean will be computed at the *k*th visit, i.e.,

 $m_k = \frac{n_1 \bar{x}_{1\cdot k} + n_2 \bar{x}_{2\cdot k}}{n_1 + n_2}$  where  $\bar{x}_{1\cdot k}$  and  $\bar{x}_{2\cdot k}$  are the arm-specific sample means. Next, the pooled standard deviation will be computed at the kth visit, i.e.,

$$s_k = \sqrt{\frac{(n_1 - 1)s_{1k}^2 + (n_2 - 1)s_{2k}^2}{n_1 + n_2 - 2}}$$

where  $s_{1k}^2$  and  $s_{2k}^2$  are the arm-specific sample variances. Finally, the standardized change scores will be defined as follows:

$$x_{ijk}^* = \frac{x_{ijk} - m_k}{s_k}$$

The standardized change scores for ERP P300 latency will be computed in a similar way and will be denoted by  $y_{ijk}^*$ .

The GST score for the change from baseline to the kth visit for the jth patient in the ith trial arm is defined as

$$(\frac{x_{ijk}^* + y_{ijk}^*}{2})$$

Note that a negative sign is applied to  $y_{ijk}^*$  since an increase in the ERP P300 latency score indicates an unfavorable response. This algorithm will be applied to each post-baseline visit. Note that the GST score calculation for each post-baseline visit is a composite of standardized change from baseline components. In order to provide a baseline value for GST for covariate purposes, the baseline GST score will also be calculated. The calculation at baseline is slightly different, using the observed baseline ADAS-Cog13 and ERP P300 latency values, instead of change from

Confidential Page 45 of 57

baseline. Those baseline measurements are standardized using the overall baseline mean and baseline pooled standard deviation for each variable.

Confidential Page 46 of 57

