### 8.3 Clinical Effect Analyses

## 8.3.1 Primary Clinical Effect Analysis - GST

The primary hypothesis is that treatment with ATH-1017 will result in a statistically significant reduction in change from baseline in the GST score (O'Brien, 1984) (combining the ADAS-Cog13 score and the change from baseline in ERP P300 at Week 26) relative to the placebo group in the mITT population. The primary analysis will test the statistical hypothesis of no difference between placebo and 70 mg ATH-1017 first and then 40 mg ATH-1017 versus placebo.

The primary analysis will use a mixed model with repeated measures (MMRM) to compare the estimated change from baseline between active treatment and placebo in the GST score. This analysis will assess whether or not there is a difference in estimated GST values between treatment groups and placebo at 26 weeks using least squares means estimates from the MMRM model, and will include terms for baseline, baseline by time interaction, and baseline by time by treatment interaction in the model. Additional terms will be included for GBA genotype, and site (with smaller sites grouped), and age. Least squares means and standard errors will be estimated from the MMRM model at Week 26. Further details relating to the primary analysis will be described in the SAP.

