#### 6.2.1 Cognitive Variables & Pharmacodynamic Variable

## 6.2.1.1 Global Statistical Test (GST) score

A composite approach will be used to facilitate the assessment of an overall change in disease status/trajectory in the trial. The GST score will be defined as a single outcome variable based on standardizing and then combining individual patient-level change from baseline cognition (ADAS-Cog13) and change from baseline in ERP P300 latency. The GST score will be determined for each patient at each time point and the resulting scores will define the efficacy outcome variable to be used in the primary efficacy analysis. A formal definition of the GST score is given in Appendix 1. The assessment will be performed as per Appendix 2 Schedule of Assessment.

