#### 6.2.1.2 Alzheimer's Disease Assessment Scale – Cognitive Subscale (ADAS-Cog13)

The ADAS-Cog13 is designed to measure cognitive symptom change in subjects with MCI as well as AD (Mohs et al, 1997). In addition to the standard 11 items present in the ADAS-Cog11 (word recall, commands, constructional praxis, naming objects and fingers, ideational praxis, orientation, word recognition, spoken language ability, comprehension of spoken language, word-finding difficulty, and remembering test instructions), the ADAS-Cog13 includes a test of delayed word recall and a number cancellation task. The test comprises 9 performance items and 4 clinician-rated items, with a total score ranging from 0 (no impairment) to 85 (severe impairment). Therefore, higher scores indicate more severe cognitive impairment. The assessment will be performed as per Appendix 2 Schedule of Assessment.

[figure not shown]

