# 10.5 Efficacy

Summary statistics will include change from baseline comparison of ATH-1017 with placebo using a two-sample t-test without baseline adjustment. All statistical tests will be carried out using a one-sided 2.5% significance level and all comparisons will be reported with 95% confidence intervals for mITT population unless otherwise stated. The comparison between ATH-1017 (40 mg and 70 mg pooled) and placebo will serve as the primary efficacy comparison. This summary will be produced for each disease type and AChEI usage within disease type also.

Confidential Page 35 of 57

No adjustments will be made for multiple comparisons.

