#### 10.5.1 Primary Analysis

NOTE: The following description for the primary analysis was prepared to implement the intention of the protocol, however in view of the early stopping of the trial this analysis will not be performed, unless the simple summary statistics suggest a finding of interest, in which case this would be performed as an exploratory analysis.

The primary analysis will use a mixed model with repeated measures (MMRM) to compare the GST score between ATH-1017 and placebo at 26 weeks. In this MMRM model, GST score (a composite of the standardized change from baseline variables) will be considered as the outcome variable and the following fixed terms: baseline value, treatment arm, visit, treatment by visit interaction, baseline by visit by treatment interaction, GBA genotype, and baseline age. The correlations among repeated observations within a patient will be accounted for by specifying an unstructured covariance matrix. The least squares mean, and treatment differences will be estimated from the MMRM model.

The MMRM model summary will contains LSMEAN, Standard Error (SE), 95% CI at each visit by treatment (ATH-1017, Placebo) will be displayed. Also, LSMEAN for ATH-1017 difference from placebo, SE, 95% CI, and p-value at Week 26.

If convergence not met for the MMRM model, GST score between ATH-1017 and placebo at Week 26 will be compared using one sided t-test 2.5% significance level.

Additionally, the GST score will be listed and summarized for all visits. This summary will be produced for each disease type and AChEI usage within disease type also. A line plot with mean GST score and 95% CI over visit by treatment arm (40 mg ATH-1017, 70 mg ATH-1017 and placebo) will be displayed.

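### SAP Appendix 1 prints the primary composite as a sum but says the sign of P300 latency alone is reversed, although both components are scored higher-is-worse

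*SAP*

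**What the plan says.** SAP 6.2.1.1 defers to the appendix for the endpoint: "A formal definition of the GST score is given in Appendix 1". Appendix 1 takes the change from baseline in ADAS-Cog13 and in P300 latency, subtracts the overall mean at the visit, divides by the pooled SD, and calls the results `x*` and `y*`. The GST score is then printed as `(x* + y*)/2`.

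The text below the formula reads "Note that a negative sign is applied to" `y*`, "since an increase in the ERP P300 latency score indicates an unfavorable response". Nothing is said about the sign of `x*`.

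On ADAS-Cog13, SAP 6.2.1.2 says: "Therefore, higher scores indicate more severe cognitive impairment". Protocol 6.2.1.2 agrees.

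Protocol 8.3.1 gives the direction of benefit: the hypothesis is that treatment "will result in a statistically significant reduction in change from baseline in the GST score" relative to placebo. SAP 10.5 says "All statistical tests will be carried out using a one-sided 2.5% significance level", but neither 10.5 nor 10.5.1 states which direction is favourable.

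On what survives early stopping, SAP 10.5.1 withholds the MMRM "unless the simple summary statistics suggest a finding of interest". The same section adds: "Additionally, the GST score will be listed and summarized for all visits".

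**The concern.** A composite of two outcomes supports an overall conclusion only if both point the same way. Here both are higher-is-worse, and centring and scaling reverse neither, so they are already aligned before they are combined. A minus on one of them sets them against each other: the score then measures half the difference between the two effects instead of their average.

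Two programmers working from Appendix 1 could therefore derive different primary scores, one from the formula and one from the note, and a reader of the GST table could not tell which was used. A benefit larger on P300 than on cognition would appear as harm in the direction set by Protocol 8.3.1. The error could also affect whether the MMRM is run, because that depends on how the simple summaries look.

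**Working it through.** **Readings of the definition.** The equation was read from the PDF, so a lost sign cannot be excluded. The note fails on each reading.

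| Reading | Score | Components | Better is | State of the note |
|---|---|---|---|---|
| 1. Sum as printed | `(x* + y*)/2` | aligned | lower, as in Protocol 8.3.1 | wrong |
| 2. Note applied, or an inner minus lost | `(x* - y*)/2` | opposed | undefined for joint benefit | followed, but its reason applies equally to `x*` |
| 3. Minus on the whole bracket | `-(x* + y*)/2` | aligned | higher, the reverse of Protocol 8.3.1 | incomplete: names only `y*` |

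A patient 1 SD better than the overall mean on both components has `x* = y* = -1` and scores -1.0, 0 and +1.0 respectively.

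**Group difference.** Let the active arm be better by *a* SD on ADAS-Cog13 and *b* SD on P300 latency. The overall mean cancels in the difference between arms, so the expected GST difference (active minus placebo) is:

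- sum: `-(a + b)/2`
- note: `-(a - b)/2`

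This needs no assumption about sample size. With a = b = 0.5 the sum gives -0.5 and the note gives 0. With a = 0.2 and b = 0.5 the sum gives -0.35 and the note gives +0.15, in the harm direction.

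**Chance that the GST mean difference points to benefit (below zero).** The documents give neither the number enrolled, nor an effect size, nor the correlation rho between components. I assume pooled active vs placebo of 10 vs 5 to 20 vs 10, and rho = 0.3.

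- SD of the score: `sqrt((1 + rho)/2)` = 0.806 (sum); `sqrt((1 - rho)/2)` = 0.592 (note)
- SE = SD × `sqrt(1/n1 + 1/n2)`: for 10 vs 5, 0.442 (sum) and 0.324 (note); for 20 vs 10, 0.312 and 0.229
- Probability = Φ(-difference/SE); for example Φ(0.5/0.442) = 87%

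| a (ADAS-Cog13) | b (P300) | Sum: 10 vs 5 | Sum: 20 vs 10 | Note: 10 vs 5 | Note: 20 vs 10 |
|---|---|---|---|---|---|
| 0.5 | 0.5 | 87% | 95% | 50% | 50% |
| 0.2 | 0.5 | 79% | 87% | 32% | 26% |
| 0.5 | 0.2 | 79% | 87% | 68% | 74% |

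For rho from 0 to 0.5, the equal-benefit figure for the sum runs from 90% to 85% (10 vs 5) and from 97% to 93% (20 vs 10). The note stays at 50%.

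**Planned size, for illustration only.** With 50 vs 25, rho = 0.3 and 0.5 SD on each component, SE = 0.806 × `sqrt(1/50 + 1/25)` = 0.197 and the non-centrality is 2.53. One-sided 2.5% power is 70% with the sum (non-central t) and 2.5% with the note. Simulating the Appendix 1 standardisation (20,000 trials) gave 71.0% and 2.9%. The plan has no power figure of its own to reproduce; its sample size was chosen empirically.

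**Baseline GST covariate.** Appendix 1 forms it from baseline values without a separate sign rule, so it inherits the ambiguity. Only reading 2 changes its content; a minus on the whole bracket merely mirrors the score.

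**The case against.** The strongest reply concerns consequence. SAP 6 makes efficacy exploratory, SAP 8 rules out any statistical conclusion from a test, and SAP 10.5.6 makes everything beyond summary statistics optional. ADAS-Cog13 and P300 latency have their own rows in Table 6, so a GST result at odds with both would be noticed. The MMRM trigger is the simple summaries in general, not GST alone. The mean plot sits in Section 10.5.1 under the note suspending the primary analysis, so its production is not certain. All of this stands and limits the harm.

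Second, cancellation occurs only under reading 2. If the code follows the printed sum, the results are unaffected, and the documents do not show which version was coded. If a minus before `y*` was lost from the formula, formula and note would agree, and the fault would be a misdirected composite rather than a contradiction. That is fair, but a defect remains on each reading and no other section repairs it.

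Third, Protocol 8.3.1 leaves further detail to the SAP, so the SAP might legitimately orient GST with higher as better. It would then have to say so for both components and for the one-sided test, and it does not.

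**Conclusion.** The concern holds. Appendix 1 gives a formula and a sign note that cannot both be followed as printed, and the note is wrong or incomplete even if a sign was lost from the formula. The algebraic consequence of coding the note is exact: equal standardised benefits give a GST difference of zero, and a larger benefit on P300 than on cognition gives a shift in the harm direction. The probabilities and power figures rest on assumed enrolment, effects and correlation, and show scale only. Because efficacy is now exploratory, the practical effect falls on the GST summaries, the t-test, the plot if produced, and in part the decision to run the MMRM. It should still be corrected before the score is derived, because the formal definition of the primary endpoint cannot at present be programmed unambiguously.

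**What to change.** Check the equation in the source document, then reconcile formula and note so that both components carry the same sign, for the post-baseline and the baseline GST.

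- **Preferred**, because it matches the printed formula and Protocol 8.3.1: keep `(x* + y*)/2`, delete the note on `y*`, state that lower is better, and state the one-sided alternative as mean GST on ATH-1017 below placebo.
- **If a minus on the whole bracket was intended**: print it, say that it applies to both components, and reverse the favourable direction consistently in the test, tables and plot.

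In either case, check the derivation code against the corrected text. The cost is a line or two of SAP text and the code check, with no effect on data collection or patients.
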